## 5. **REGISTRATION PROCEDURE (VISIT 1)**

#### 5.1 Screening procedures

The PI must keep a screening and enrolment log of all patients being considered for PROMIS. These logs will be provided by the MRC CTU at centre accreditation.

#### 5.2 Obtaining written informed consent

Men at risk of prostate cancer who have been advised to have a prostate biopsy will be invited to join the study. Potential participants will be approached by a study clinician or research nurse (who is a member of their direct clinical care team). Patients interested in participating in the study, will be given a PIS to read and at least 24 hours, as per national standards, to consider the study. Patients will be given email, telephone and postal contact details if they wish to address any queries or concerns. It will be emphasised that were patients to refuse participation, their continued care will not be affected in any way. **Consent must be obtained by an authorised clinician before any trial-specific patient assessments are carried out**.

#### 5.2.1 Pre-registration investigations

- **PSA**: it is a requirement of the eligibility criteria that a PSA test has been carried out within 3 months of registration. Results are required for registration. If this test has been done as part of standard care and within the 3 month timeframe, there is no need to repeat this test. However, if the PSA test has not been completed, it should be carried out after consent has been obtained and prior to registration.
- Free/Total PSA: If this test has been done as part of standard care within 3 months of registration and the results are available, then there is no need to repeat this test. However, if the Free/Total PSA test has not been completed and it is possible to collect, it should be carried out after consent has been obtained and prior to registration.
- **Blood and urine sample collection**: Only to be taken if the patient has agreed to this option on the consent form. The blood samples should be taken after consent and before the combined biopsy procedure. Urine samples should be taken before and after DRE (see below).
- **Digital rectal examination (DRE)**: it is a requirement of the eligibility criteria that a patient must have suspected stage ≤ T2 on rectal examination (organ confined). Results are required for registration. DRE should be carried out after consent has been obtained and prior to registration if:
  - $\circ \quad$  a consenting patient is having urine samples collected, or
  - $\circ$  DRE has not been already been completed within the 6 months prior to registration.

However, if the patient is not having urine samples collected and DRE has been done as part of standard care within the 6 month timeframe there is no need to repeat this test.

• EQ-5D (Appendix III): this should be completed after consent has been taken.

#### 5.3 Visit 1: Registration

Please confirm patient eligibility and complete the registration form before telephoning the MRC CTU. During this telephone call, the patient will be allocated a unique identification number which will be used in all correspondence. Confirmation of the details provided at registration will be sent within one working day of entry.

## 6. PROCEDURES, ASSESSMENT & FOLLOW-UP (VISITS 2-4)

All patients will have a MP-MRI of the prostate as the index test. At a separate visit, patients will undergo two biopsies combined within the same procedure (see Trial Schema 1.2): the template prostate mapping (TPM) and a TRUS guided biopsy of the prostate.

The MP-MRI should be done as soon as possible following patient registration. The two biopsies will be done under the same general/spinal anaesthetic and should be carried out within a maximum of 3 months after the MP-MRI. TPM will be performed prior to the TRUS guided biopsy (within the same procedure).

A follow-up visit will occur after the biopsies where results of all tests will be given to patients (usually within 4 weeks of the combined prostate biopsy (CPB) procedure. This will be the end of patient follow-up in this study.

#### 6.1 Visit 2: MP-MRI

The MP-MRI will be carried out in a 1.5 or 3.0 Tesla scanner with the patient in the supine position. T2, DW and DCE scans will be acquired.

The primary analysis will be based on the local site radiology report. Clinical details including PSA and DRE findings will be known to the reporter. In addition, to determine inter-observer variability and as a quality control measure, double-reporting will be carried out centrally by a number of designated radiologists who will also know clinical details of the case.

Scans will be reported to the MRC CTU on the MRI case report form (CRF) and kept locally by the local site radiologist. Radiologist should refer to the MRI Standard Operating Procedure (SOP). Scans deemed unreadable should be repeated in the same patient whenever possible and appropriate to do so. Cases where MRI scans could not be done/are not readable and are not repeatable should be noted on the MRI CRF that is sent to the MRC CTU (Please see Withdrawal section 6.10 for further information).

An overall whole prostate score will be given (1-5) to indicate the probability of clinically significant cancer:

- Highly likely benign (1).
- Likely benign (2).
- Equivocal (3).
- Likely malignant (4).
- Highly likely malignant (5).

For the primary outcome, an overall score of 3 or more will be used to indicate the possible presence of clinically significant cancer. This reflects the level at which further tests (e.g. biopsy) would be considered if MP-MRI were to be introduced into the diagnostic pathway in the future.

Each reporter will have access to a workstation with mean curve software to be used in the scoring of suspicious lesions (up to a maximum of 6). Images will be reported in sequence: T2  $\rightarrow$  T2+DW  $\rightarrow$  T2+DW+DCE and a separate report produced for each combination of sequences.

For sector analysis, the prostate will be divided into 12 regions of interest (ROI):

- Apex: Right/Left & Anterior/Posterior.
- Mid: Right/Left & Anterior/Posterior.
- Base: Right/Left & Anterior/Posterior.

Radiologists will use the 1-5 score for each ROI.

For each lesion found, the following will be recorded:

- Longest axial diameter.
- Lesion volume.
- Apparent Diffusion Coefficient (ADC).
- DCE-MRI curve shape.

To assist the sector analysis, radiologists will draw the locations of lesions on the 27 ROI diagram (See Appendix IV) which incorporates the 1.7cm line from the back of the prostate gland. This will involve declaring the suspected positives only. The radiologist will also report the likely co-ordinates at which they would expect cancer to be positive on TPM.

MP-MRI scans will be reported on the MRI CRF and filed with the MRC CTU and with the local radiologist before the biopsy procedures are carried out. **These results must be kept blinded. Results must not be reported to the clinician performing TPM/TRUS biopsies.** Reports will only be released to the study doctor by the MRC CTU after the CPB procedure has been performed (see section 6.8). Please refer to the PROMIS MRI SOP for more detail on this procedure.

#### 6.2 Visit 3: Combined Prostate Biopsy (TPM + TRUS)

TPM will be performed first under the same general/spinal anaesthetic as the TRUS guided biopsy. The biopsy procedure is combined to reduce patient burden (two visits, two procedures) and also to minimise drop out of patients between biopsies. Biopsies will be taken every 5mm throughout the prostate using a template grid placed over the perineum. Biopsies will be oriented and individually identified to facilitate later correlation of results with imaging.

TRUS guided biopsy of the prostate is to be performed after TPM, under the same general/spinal anaesthetic. This helps ensure results are obtained for the reference test in a biopsy naïve gland that has not undergone swelling and distortion to allow better post-study comparisons of the TPM and MRI findings. It also minimises the risk of infection.

The surgeon performing the CPB procedure will be blind to the MRI results. TRUS guided biopsies will be done in the left lateral position. 10-12 core biopsies will be taken as per national guidelines. Each core will be identified and potted separately. The TPM and TRUS biopsy sets from a particular patient will be sent to different pathologists to minimise bias. The pathologists will independently report results to the MRC CTU on the separate TPM and TRUS electronic CRFs. Please refer to the PROMIS Combined Biopsy SOP.

#### 6.3 Visit 4: End of study visit

The last study visit should take place within approximately one month of the CPB procedure. At this visit the clinician will discuss the results of all 3 study tests (MP-MRI, TPM biopsy and TRUS biopsy) with the patient. Any side-effects of the tests experienced by the patient can be discussed. This visit marks the end of the study for the patient. Patients will be managed according to standard care in view of the results of the study tests.

#### 6.4 Additional diagnostic tests

Subject to securing future funding, additional diagnostic tests will be included for evaluation of the translational objectives in this study:

- Pre and Post DRE urine (including PCA3, TMPRSS-ERG gene fusion, MSMB): on day of consent (Visit 1).
- Blood for serum and germ-line DNA: for biobanking and analysis of named biomarkers (kallikrein panel, PTEN glycoprotein panel) on day of consent or MP-MRI (Visit 1 or Visit 2).
- 3-D ultrasound volume file and radio-frequency back scatter files including Histoscanning™: immediately prior to TPM and TRUS guided biopsies at time of general/spinal anaesthetic (Visit 3).

Patients can opt out of these additional diagnostic tests if they wish, without compromising the overall primary objectives of the study as they can continue to have the MP-MRI, TPM and TRUS biopsy.

#### 6.5 Long-term follow up

The group of men who consent to participate in this study will represent a uniquely characterised group. The long term outcomes of the PROMIS cohort of men will be of interest and contribute to our understanding of the epidemiology of prostate cancer. Whilst the trial is one that aims to validate MP-MRI as a diagnostic test, men who specifically consent to longer term data collection will be flagged and followed-up using the Office for National Statistics and NHS databases (see PROMIS Registration Consent Form). For example, linkage to Hospital Episode Statistics (HES) may give valuable information on further diagnoses, treatments and outcomes beyond the timeframe of the study for future analyses.

Consenting men may additionally be contacted in future to assess their willingness to respond to questionnaires. This allows the potential for research that would complement the planned long-term follow up in terms of health status, for example picking up future biopsies not included in HES, and allow assessment of quality of life.

#### 6.6 Procedure training, quality control and quality assurance

#### 6.6.1 MP-MRI

All radiologists from non-UCLH centres working on PROMIS will attend UCLH for a minimum of one training day on the conduct and reporting of MP-MRI. Only radiologists attending the training day (or other approved training programme if they cannot attend the training day) will be approved for reporting MP-MRIs within this trial. Quality control (QC) and quality assurance (QA) of the MP-MRI will be outsourced to an independent commercial partner after a process of tender.

#### 6.6.2 CPB procedure

Training will be provided to all centres to conduct TPM. All clinicians carrying out template biopsies will be required to carry out the procedure to the standard laid down in this protocol:

- Any number of credentialed clinicians at each centre may carry out this procedure.
- Each clinician carrying out the combined procedure will need to observe a minimum of three template biopsies at a training centre (Basingstoke or UCLH).
- Each clinician will then need to be proctored for the first 6 cases by an approved expert proctor. This may be extended at the discretion of the proctor.

Clinicians will be signed off for non-proctored cases by an expert proctor. Only clinicians approved through this programme can conduct the CPB procedure for the purpose of this study.

#### 6.7 Data collection and returns

Table 2 shows the case reports forms (CRF) that are to be collected at each visit. An additional SAE form will be provided for completion as required during the study (see section 7). Please refer to PROMIS CRF completion guidelines for further details.

CRF	Screening, Consent & Registration Visit 1	MP-MRI Visit 2	CPB Visit 3	Follow-up results Visit 4
Registration	Х			
EQ-5D Questionnaire	Х	Х	Х	Х
MP-MRI Reporting Form		Х		
CPB Procedure Checklist			Х	
TPM Reporting Form			Х	
TRUS Reporting Form			Х	
End of Study				Х
SAE	Complete as required at any time following patient registration			
Withdrawal Form	Complete as required at any time following patient registration			

#### Table 2: Data collection timelines

#### 6.8 Blinding

#### 6.8.1 Blinding of MP-MRI results

In order to make sure that the result of the MP-MRI does not influence the conduct of the biopsy, the results of the MP-MRI will not be revealed to either the men having the biopsies nor to the clinicians undertaking the biopsies until after the results of the TRUS guided biopsy and TPM are available (with one exception for unblinding given below). This blinding is necessary to prevent the results of the MP-MRI leading to some change in how the biopsies are conducted and to protect against the possibility that MP-MRI may be made to look either better or worse than it truly is in detecting and/or ruling-out significant cancer. It is essential that

the key reference test (TPM) is done in a truly systematic way so that the MP-MRI prediction can be compared to the appropriate tissue sample. Whilst accepting that TRUS biopsies under general/spinal anaesthetic may be carried out better than standard care (under local anaesthetic), it is also important that the conduct of TRUS guided biopsies is also blind to the MP-MRI so no targeting of suspicious areas occurs.

Radiology reports will be submitted directly and securely to MRC CTU. The CPB procedure will be conducted by someone other than the MRI reporter. Please refer to the PROMIS MRI SOP for more detail.

#### 6.8.2 Blinding of biopsy results

To minimise bias between assessment of the TPM and TRUS biopsies, cores from TPM and TRUS biopsy procedures will be sent to different pathologists who will independently report results to the MRC CTU. Please refer to the PROMIS Combined Biopsy SOP for more detail.

#### 6.8.3 Unblinding

For safety purposes, the results will be unblinded if the MP-MRI reveals apparent T4 prostate cancer or involved lymph nodes or colorectal/bladder invasion. This information will be provided to the treating clinician for appropriate clinical decision making. For some of these patients, the template mapping biopsies may be considered by the clinician as not providing useful additional clinical information and would, therefore, not be warranted, although TRUS guided biopsies are usually performed. Patients in this situation will exit the study and standard care followed. Further patients will be recruited (see section 9.2.4) to maintain the number of patients undergoing the study procedures (MP-MRI & CPB procedure).

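### The single exception to the MRI blind is a closed list that leaves out apparent bone or other non-nodal distant metastasis

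*Protocol*

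**What the plan says.** Every man has a prostate MP-MRI before biopsy (section 6: "All patients will have a MP-MRI of the prostate as the index test"). The combined template and TRUS biopsy "should be carried out within a maximum of 3 months after the MP-MRI".

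The scan result is withheld in between. Section 6.1 bars giving it to the clinician who performs the biopsies and adds: "Reports will only be released to the study doctor by the MRC CTU after the CPB procedure has been performed". Section 6.8.1 is stricter on timing: it withholds the result from the men and the biopsy clinicians until both biopsy results are available, "with one exception for unblinding given below".

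Section 6.8.3 supplies that exception. For safety purposes, "the results will be unblinded if the MP-MRI reveals apparent T4 prostate cancer or involved lymph nodes or colorectal/bladder invasion", and the treating clinician is then told. The reason given is that for some of these men "the template mapping biopsies may be considered by the clinician as not providing useful additional clinical information", "although TRUS guided biopsies are usually performed". The section continues: "Patients in this situation will exit the study and standard care followed". Exiting men are replaced, so the number completing the study procedures is kept.

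**The concern.** The exception rests on a general safety argument: when the scan suggests advanced disease, the clinician should know before mapping goes ahead, because mapping may no longer be worth doing. That argument applies at least as well to apparent bone or other distant metastasis. Yet the list has no such item, and no open wording that would let a radiologist or the trials unit add one.

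A man in that position meets no trigger, so the default rule applies. His report stays blinded, and he has a general or spinal anaesthetic and mapping at 5 mm intervals that his clinician might have judged unnecessary. What is at stake is an avoidable procedure and a delay in telling the clinician about an important finding.

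**Working it through.** The protocol states no figure for this point, so the check applies the written rules to one case and then sizes the consequence from the protocol's own numbers.

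**Applying the rules.** Take a man with apparent bone metastasis on MP-MRI and no apparent T4, no involved node and no bowel or bladder invasion.

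1. Section 6.8.3: none of the three triggers is met.
2. Section 6.8.1: there is only one exception, so no other route to early release is provided.
3. Section 6.1: the report is released only after the CPB.
4. Section 11.3 leaves the clinician free to depart from the protocol in the patient's interest, but a clinician who has not seen the report has no reason to use that freedom.

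The gap is narrower than all distant disease. Section 6.8.3 does not restrict involved nodes by region, so distant nodes already trigger release. What remains is bone and other non-nodal sites.

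**Length of withholding.**

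- Under 6.1, release follows the CPB, which may be up to 3 months after the scan: up to 3 months.
- Under 6.8.1, release waits for the biopsy results. Section 6 says results are usually given within 4 weeks of the CPB: 3 months + 4 weeks = about 4 months. Because of the word *usually*, this is not a strict maximum.

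**Avoidable burden per affected man.** TRUS biopsy is usually still performed after unblinding (6.8.3), so only the mapping and its anaesthetic count.

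- Procedure time (11.2): mapping takes 30–40 minutes; TRUS alone takes 15.
- Anaesthetic (11.2): general/spinal for mapping; local for TRUS in usual practice.
- Urinary retention: 5% with mapping (2.5, Table 3; 1 in 20 in 11.2) against 1% with TRUS (11.2, Table 3) or 1–2% (2.5).
  - Excess = 5% − 1% = 4 points, or 5% − 2% = 3 points.
  - One extra retention per 1/0.04 = 25 to 1/0.03 ≈ 33 affected men.
  - Assumption: mapping's 5% also holds for the CPB, since 11.2 expects no significant additive risk.
- Sepsis: mapping alone carries less than 0.5% (2.5, 7.1), so omitting it would avoid little sepsis.

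**Number of affected men.** The protocol gives no rate and none is assumed. Entry requires PSA of 15 ng/ml or less and suspected stage T2 or less on rectal examination (4.1). This makes the case unlikely but does not exclude it, since no staging for distant disease is required. The number could be zero.

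**The case against.** The strongest reply is that the situation may never arise. The index test is a scan of the prostate, and the outputs that 6.1 lists (whole-gland score, regional scores, lesion measurements, location diagram) all concern the gland. The field of view is not stated. The existing triggers do reach outside the prostate, but mostly as local extension, and none of them shows that the skeleton would be covered or reported. This stands as a condition: the point has force only if the scan shows such disease and the radiologist notes it. However, 6.8.3 already expects nodal, bowel and bladder findings to be acted on, and the entry criteria that make metastasis unlikely make those findings unlikely too. The protocol still provided for them.

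A second reply is that the MRI SOP, to which 6.1 and 6.8.1 refer for detail, may say how to handle a serious finding beyond the gland. It is not at hand and may do so. But the protocol allows one exception only, so an SOP that added another would conflict with it.

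Third, the site radiologist holds the report, so the information is not out of reach. That is true, but the protocol sets out no route for using it in this case.

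Fourth, the harm is modest. It is: mapping adds one procedure and retention that 2.5 describes as self-limiting.

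A reader might infer that such a man would be spared biopsy altogether. The documents do not support that, because TRUS biopsy is usually still done after unblinding, and 6.8.3 says only that mapping may be judged unwarranted in some men.

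**Conclusion.** The gap is real on the protocol's own wording. The only exception to the MRI blind is a closed list whose safety reason covers a finding that the list omits. For an affected man the report would be withheld for up to 3 months (6.1) or about 4 months (6.8.1). The avoidable burden is template mapping with its general/spinal anaesthetic and 3 to 4 points more self-limiting retention.

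This is a low-frequency patient-safety point that may affect no one. It assumes that the scan can show bone or other non-nodal distant disease, that the radiologist records it, and that the protocol's single exception is applied as written.

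Two stronger readings should be resisted. One is that the blind distorts the results: it does not, because the group is at most very small and accuracy estimates are essentially unaffected. The other is that the study as a whole certainly leaves these men unprotected: without the SOP, only the protocol's wording can be judged. The change is worth making because it costs so little.

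**What to change.** Add *or apparent bone or other distant metastasis* to the triggers in 6.8.3, and let these men follow the existing unblinding, exit and replacement route. The MRI SOP should then be checked for consistent wording.

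The cost is one phrase. Possibly a few more men would be unblinded, exit and be replaced; sections 6.8.3 and 9.2.4 already provide for replacement, so the target number with all three tests is kept. An exiting man who still needs a TRUS biopsy would usually have it under local rather than general/spinal anaesthetic.

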#### 6.9 Loss to follow-up

As the period of follow-up is relatively short, at approximately 4 months, there should be minimal problems with loss to follow-up in this study. Incomplete or late CRFs will be requested from the centre by the PROMIS Trial Manager at the MRC CTU. Circumstances and reasons why a patient is lost to follow-up should be detailed in writing to the Trial Manager and a copy filed in the patient's records.

#### 6.10 Withdrawal

In consenting to the study, patients are consenting to study monitoring, imaging and biopsy procedures, followup, data collection and analysis. Patients are allowed to withdraw consent at any stage, however this is expected to be a very rare occurrence. Withdrawal may be complete (i.e. from further study procedures and any follow up), or partial (e.g. from study procedures but allowing the possibility of further follow up). All communication surrounding the withdrawal should be noted in the patient's records, and where withdrawal is complete no further PROMIS CRFs should be completed for that patient. Data up to the time of withdrawal can be included in the study if anonymised.

The MRC CTU should be informed of any patient withdrawals by sending in a completed Withdrawal Form. Patients registered into PROMIS but for whom there is no subsequent MP-MRI result or will not go on to have one or more of the study procedures should be withdrawn from the study and any remaining procedures.

